5.1. Primary Endpoint(s)

- Pharmacokinetic parameter "Cmax": Dose-dependent changes in Cmax of several doses of combined DMT & Harmine.
- Pharmacokinetic parameter "Area under the curve (AUC)": Dose-dependent changes in AUC of several doses of combined DMT & Harmine.
- Pharmacokinetic parameter "T1/2": Dose-dependent changes in T1/2 of several doses of combined DMT & Harmine.
- Incidence of Treatment-Emergent Adverse Events: Dose-dependent changes in incidence of adverse drug reactions.
- Blood count (Lab biochemistry): Changes from baseline in blood count.
- Clinical chemistry (Lab biochemistry): Changes from baseline in any clinical chemistry parameter with potential clinical relevance.
- Blood coagulation (Lab biochemistry): Changes from baseline in blood coagulation.
- QT interval (12-lead Electrocardiogram [ECG]): Dose-dependent changes of QT intervals assessed by clinical 12-lead ECG).
- Blood pressure: Dose-dependent changes in systolic and diastolic blood pressure.
- Heart rate: Dose-dependent changes in heart rate.

- Temperature: Dose-dependent changes in body temperature (in °C).
- Genotyping: Collection of saliva-samples to determine genetic polymorphisms.
- Subjective effects: Dose-dependent changes in trajectories of subjective effects.

5.2. Secondary Endpoint(s)

- Aliveness - Behavioral Task: Validated instrument developed to assess dose-dependent changes in perceived aliveness.
- Heart-rate-Variability, Physical Activity, Sleep Patterns: Wearable device for continuous sensor assessments.
- Heart-rate-variability: Occurrence of dose-dependent changes in heart-rate-variability assessed by a wearable device.
- Physical Activity: Occurrence of dose-dependent changes in physical activity assessed by a wearable device.
- Sleep Patterns: Occurrence of dose-dependent changes in sleep patterns assessed by a wearable device.

5.3. Pharmacokinetic Endpoints

Blood samples for PK analysis of DMT and harmine will be taken according to the study design given in the protocol.

The following PK parameters will be calculated for DMT and harmine (if possible) from the plasma concentration-time data as decided by the pharmacokineticist.

5.3.2 AUC

Definition: Concentration-time profile from time zero to the time of the last quantifiable concentration

Method of determination: Linear/Log trapezoidal method.

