3.1.1. Initial titration period

We will administer the sublingual formulation with varying fixed starting doses of DMT and harmine and let the study participants increase the total dose of DMT and harmine in 20 minute intervals at fixed increments up to two times. We will test 7 different dosing conditions with varying DMT:harmine ratios during the first 4 days (see figure 1). The tested ratios range between 0-120 mg DMT and 0-180 mg harmine. The dose ratios will be administered in a sequential order with two different sequences in two arms, and the DMT or harmine only condition will be tested on the fourth study day; this is done to further clarify if DMT alone is capable of inducing its effects with routes other than intravenous administration or inhalation. The DMT/harmine only condition is the only one that is exclusive for one of the two study arms. The rationale behind this dosing scheme is to find the optimal dose of harmine and DMT independently of each other by taking account for order/PD habituation and linear/non-linear drug-drug-interaction effects and to establish the optimal dosing for the future studies based on PK/PD analytics.

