7.3. Statistical Analyses

7.3.1. Pharmacokinetic Analysis

7.3.1.1. Pharmacokinetic Parameters

To assess the pharmacokinetics of DMT/harmine dose formulations, the PK parameters detailed in Section 5.3 will be listed and summarized for subjects in the PK analysis sets (as defined in Section 4.2 and Section 4.4.1). Missing values will be handled as detailed in Section 6. Each PK parameter will be summarized by dose combination, and will include the set of summary statistics as specified in the table below:

Table 1. PK Parameters to be Summarized Descriptively

Parameter	Summary Statistics
AUC, Cmax	N, arithmetic mean, median, cv%, standard deviation, minimum, maximum, geometric mean and geometric cv%.
T $\frac{1}{2}$	N, median, minimum, maximum.

There will be 1 summary table presenting all PK parameters. This will include data from all dose combinations. The treatment subheading will include the dose condition and dosing regimen information.

To assess the relationship between the PK parameters and dose, dose normalized AUC and Cmax will be plotted against dose.

If the conditions listed in Section 3.2 are met, AUC (if data permit) and Cmax will be analyzed using mixed-effects models for all administered dose combinations. The purpose of these analyses is to obtain estimates of the intra-subject variation to assist in the planning of future studies.

Supporting data from the estimation of 'T $\frac{1}{2}$ ' will be listed by analyte where applicable: terminal phase rate constant (k_{el}); goodness of fit statistic from the log-linear regression (r^2); the percent of AUC based on extrapolation, and the first, last, and number of time points used in the estimation of k_{el} . This data may be included in the clinical study report.

Presentations for DMT and harmine concentrations will include:

- concentration data according to dose conditions, number of doses administered, and nominal time points for individual subjects in the form of a table of concentration data organised to present the effect of dose parameters and time for individuals. Conventional summary statistics for concentration data above the lower limit of quantification will accompany these results.
- plots of median concentrations against nominal time post-dose by dose combination.
- boxplots of dose-normalized AUC and Cmax for each dose combination and number of administered doses per dose combination.
- plots of mean concentrations against nominal time post-dose by dose combination.

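### The only AUC defined stops at the last quantifiable concentration, so its window shortens as exposure falls and dose-normalised AUC can rise with dose under exactly linear kinetics

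*SAP*

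**What the plan says.** Section 5.3.2 gives the one AUC definition in the plan, "Concentration-time profile from time zero to the time of the last quantifiable concentration", with the "Linear/Log trapezoidal method". I read this as the area under that profile, that is AUC0-last. No AUC to infinity and no AUC over a fixed common window is defined.

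This AUC is used in several places:

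- Section 5.1 lists as a primary endpoint "Dose-dependent changes in AUC of several doses of combined DMT & Harmine".
- Section 7.3.1.1 says: "To assess the relationship between the PK parameters and dose, dose normalized AUC and Cmax will be plotted against dose". It adds "boxplots of dose-normalized AUC and Cmax for each dose combination and number of administered doses per dose combination".
- Section 3.1.1 explains the dosing scheme partly as a way to account for "linear/non-linear drug-drug-interaction effects".

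Section 7.3.1.1 also lists "the percent of AUC based on extrapolation" among the data supporting the half-life estimate. That presupposes an extrapolated AUC, but none is defined. No limit or reading rule is attached, and the listing is only optional in the study report. Section 5.3.4 allows further PK analyses at discretion.

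**The concern.** With a fixed LLOQ, a session with lower concentrations has an earlier last quantifiable time (tlast). AUC0-last then covers a shorter window and a smaller fraction of the true area. Dividing by dose does not remove this. The bias runs one way: dose-normalised AUC is too low where exposure is low, which looks like more-than-proportional exposure.

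The design sets very different exposures side by side (0–120 mg DMT, 0–180 mg harmine, and a DMT-only condition). The SAP introduction describes intense first-pass breakdown of DMT by MAO, so DMT without the inhibitor is the condition most likely to sit near the LLOQ. At stake is how the dose-normalised plots and boxplots are read when doses are chosen for later studies.

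**Working it through.** The plan states no figure that could be reproduced here, so the check is whether strictly linear kinetics give a flat dose-normalised AUC0-last.

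**From the SAP:** the AUC definition and trapezoidal rule (5.3.2); a starting dose plus up to two increments 20 min apart (3.1.1); 15 blood samples over 24 h, and vital-sign times of 0, 20, 40, 60, 85, 120, 150, 180, 240, 300, 540 and 1440 min (3.1, Study Design).

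**Assumed:** LLOQ, half-life, blood-sampling times and individual dose levels. The times and dose levels may be in figures that are not reproduced in the text at hand.

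**Analytic check (bolus, continuous sampling).** True AUC = C0/k. The area after concentration reaches the LLOQ is LLOQ/k, so the missed share is LLOQ/C0. With R = C0/LLOQ at the top dose and a 4-fold dose range, the low-to-high ratio of dose-normalised AUC0-last is (1 − 4/R)/(1 − 1/R). The true ratio is 1.00.

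- R = 10: 0.600/0.900 = 0.67
- R = 20: 0.800/0.950 = 0.84
- R = 50: 0.920/0.980 = 0.94
- R = 100: 0.960/0.990 = 0.97
- R = 500: 0.992/0.998 = 0.99

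**Sampled check.** One-compartment model, absorption half-life 15 min, elimination half-life 1, 1.5 and 2 h, linear/log trapezoid to the last sample at or above the LLOQ. Setting A: single dose, vital-sign times. Setting B: three equal doses 20 min apart, 15 assumed times (0, 20, 40, 60, 75, 85, 105, 120, 150, 180, 240, 300, 420, 540, 1440 min). Cells give AUC0-last divided by true AUC for half-lives 1 / 1.5 / 2 h.

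| Cmax/LLOQ | Setting A | Setting B |
|---|---|---|
| 5 | 0.813 / 0.797 / 0.788 | 0.768 / 0.848 / 0.763 |
| 10 | 0.896 / 0.867 / 0.788 | 0.874 / 0.848 / 0.877 |
| 20 | 0.938 / 0.867 / 0.939 | 0.928 / 0.932 / 0.934 |
| 50 | 0.938 / 0.968 / 0.939 | 0.968 / 0.966 / 0.934 |
| 100 | 0.938 / 0.968 / 0.939 | 0.968 / 0.966 / 0.934 |

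Spurious gap = 1 − (low recovery / high recovery):

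- 20 against 100 (5-fold span): A 0, 10, 0%; B 4, 4, 0%.
- 10 against 50 (5-fold span): A 4, 10, 16%; B 10, 12, 6%. The 16% arises because tlast jumps across the empty stretch from 300 to 540 min (1 − 0.788/0.939). With a sample at 420 min, B gives 6%.
- 5 against 100 (20-fold span): A 13, 18, 16%; B 21, 12, 18%.

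**Wider grid** (setting B times and dosing, absorption rate 3/h, doses 30/60/90/120, half-life 0.5–4 h, top Cmax/LLOQ 10–1000). The 30-to-120 ratio ran from 0.73 to 1.00, with no distortion in 8 of 24 scenarios. With top Cmax/LLOQ of 50 or more and half-life of 2 h or less it was 0.94–1.00. Lower values needed a top Cmax only 10–20 times the LLOQ (for example 0.73 and 0.83 at half-life 1 h), or a 4 h half-life with tlast jumping from 9 to 24 h (0.78).

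**After the fix.** AUC0-inf = AUC0-last + Clast/kel recovers 98–99% throughout in both settings, on noise-free data. At 5 times the LLOQ the extrapolated share is already about 14–23%. A common window that is quantifiable in every condition gives a ratio of exactly 1.00 when profiles are proportional.

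**The case against.** AUC0-last is a standard parameter, and nothing formal depends on it. Sections 3.1 (Statistical Hypotheses) and 7.2 anticipate no formal tests, unless conditions for within-subject analysis are met. The optional mixed model serves to estimate intra-subject variation, and the phrase on linear and non-linear interaction is design rationale, not a planned proportionality test. Dose-normalised Cmax, which truncation does not touch, is plotted beside AUC. The extrapolated share and the last time point used for kel are listed, and individual profiles are plotted, so an alert reader could see the problem. All of this stands and limits the weight of the point. It does not remove it: these items disclose the truncation without correcting it, and discretionary extra analyses would be chosen after the data are seen.

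A reader might infer that truncation could manufacture a harmine effect, or that a distortion near 20% is to be expected. The documents support neither. A comparison of 5 with 100 times the LLOQ already implies a 20-fold exposure difference; an 18% loss in the low condition would show it as 20/(1 − 0.18) ≈ 24-fold. DMT alone is one condition, in one arm, on day 4.

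The remedy also has limits. The kel estimate depends on points judged terminal and on adequate data (5.3.3), and a tight extrapolation limit could exclude the very sessions concerned. The common-window AUC must therefore carry much of the correction.

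**Conclusion.** The point holds as a possibility with a known direction. Used alone and dose-normalised, AUC0-last can make exposure look more than proportional to dose when it is not.

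For half-lives of 1–2 h and a top Cmax of 50–100 times the LLOQ, the distortion over a 4- to 5-fold span is mostly 0–10%. It goes somewhat higher when the low condition peaks near 10 times the LLOQ or tlast crosses a wide sampling gap. It is about 12–21% for 5 against 100 times the LLOQ. A top Cmax of only 10–20 times the LLOQ would also give large values. With a sensitive assay it may be nil.

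All sizes rest on an assumed one-compartment model, LLOQ, half-lives and sampling times. No error rate is affected, and a large harmine effect would be modestly exaggerated rather than created. The change is worth making because it is cheap and AUC is a listed primary endpoint.

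**What to change.** In section 5.3.2:

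1. Define AUC0-inf = AUC0-last + Clast/kel, with a maximum extrapolated share stated in advance.
2. Define an AUC over a window common to all conditions being compared.
3. Keep AUC0-last as a supportive parameter.

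In section 7.3.1.1, use AUC0-inf for the dose-normalised plots and boxplots. Where any condition in a comparison fails the limit, or kel cannot be estimated, use the common-window AUC for every condition in that comparison, so that the two measures are never mixed. List tlast by condition.

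The cost is some SAP wording and one or two derived variables, since kel and the extrapolated share are already planned. The downsides are that AUC0-inf will be unavailable in some low-exposure sessions and that the common window is set by the lowest-exposure condition. The common window is also exact only when profiles have the same shape. If harmine lengthens the DMT half-life, it would understate that difference and should be read as a partial AUC.

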5.3.3 T 1/2

Definition: Terminal elimination half-life.

Method of determination: $(\ln 2)/k_{el}$, where k_{el} is the terminal phase rate constant calculated by a linear regression of the log-linear concentration-time curve. Only those data points judged to describe the terminal log-linear decline will be used in the regression. This parameter can be calculated if permitted by the available data.

5.3.4 Reporting pharmacokinetic data

The PK parameters will be summarized descriptively by dose combination condition in accordance with the Standard Operating Procedures (SOP).

Individual and average blood plasma concentrations for DMT and harmine will be plotted separately against sampling time points for each dose combination. These plots will be used to help understand the relationship between the plasma PK parameters and dose. Additional PK analyses may be performed if deemed appropriate.

5.4. Safety Endpoints

The following data are considered in standard safety summaries (see protocol for collection days and list of parameters):

- Adverse events
- Laboratory data
- Vital signs (blood pressure, heart-rate)
- ECG results

5.4.1. Adverse Events

Adverse events (AEs) will be recorded as defined in Section 6.2 of the protocol.

5.4.2. Laboratory Safety Tests

Safety laboratory tests will be performed as described in the protocol.

To determine if there are any clinically significant laboratory abnormalities, the haematological, clinical chemistry (serum) safety tests will be assessed against the criteria specified in the sponsor reporting standards. The assessment will consider whether each subject's baseline test result is within or outside the laboratory reference range for the particular laboratory parameter.

5.4.3. Vital Signs

Single supine measurements will be taken at times detailed in Sections 3.2-3.3 of the protocol.

The following vital signs endpoints will be determined:

- The maximum decrease and increase from baseline (pre-dose) over all measurements taken post-dose for supine systolic and diastolic blood pressures.
- The maximum decrease and increase from baseline (pre-dose) over all measurements taken post-dose for body temperature.

The maximum increase from baseline (eMAX) will be calculated by first subtracting the baseline value from each post-dose measurement to give the change from baseline. The maximum of these values over the respective period will then be selected, except in the case where a subject does not show an increase. In such an instance, the minimum decrease should be taken.

Similarly, the maximum decrease from baseline (eMIN) will be determined by selecting the minimum value of the changes from baseline. In cases where a subject does not show a decrease, the minimum increase should be taken.

5.4.4. ECG

ECGs will be recorded at multiple timepoints throughout the acute measurement period, starting from the pre-dose baseline of each study visit when doses are administered, as detailed in Section 3.3 of the protocol.

The QT, QTc, PR, RR, QRS and heart rate will be recorded at each assessment time.

If not supplied, QTcF will be derived using Fridericia's heart rate correction formula:

$$QTcF = QT / (RR)^{1/3} \quad \text{where } RR = 60/\text{HR} \text{ (if not provided)}$$

If not supplied, QTcB will be derived using Bazett's heart rate correction formula:

$$QTcB = QT / (RR)^{1/2} \quad \text{where } RR = 60/\text{HR} \text{ (if not provided)}$$

The maximum absolute value (post-dose) and the maximum increase from baseline for QTcF, QT, heart rate, PR and QRS, will be determined over all measurements taken post-dose for QTcF, PR and QRS.

The maximum increase from baseline will be calculated by first subtracting the baseline value from each post-dose measurement to give the change from baseline. The maximum of these values over

the respective period will then be selected, except in the case where a subject does not show an increase. In such an instance, the minimum decrease should be taken.

5.5. [REDACTED]

CCI

5.5.1. [REDACTED]

5.5.2. [REDACTED]

5.5.3. [REDACTED]

6. HANDLING OF MISSING VALUES

A designated biostatistician may apply multiple data imputation techniques, including pairwise deletion and imputation, and compare the approaches for quality control purposes at their own discretion.

6.1. Concentrations below the Limit of Quantification

In summary statistics for pharmacokinetic assayed values below the lower limit of quantification (LLOQ) will be set to zero. The imputations (e.g., $\frac{1}{2}$ LLOQ) may be considered in other analyses if deemed appropriate. Values below the LLOQ will be reported as “<LLOQ” where LLOQ will be replaced with the numerical value for the lower limit of quantification. The LLOQ for various PK and concentrations will be noted in all tables and listings.

6.2. Deviations, Missing Concentrations and Anomalous Values

In summary tables and plots of median profiles, statistics will be calculated having set concentrations to missing if one of the following cases is true:

1. A concentration has been collected as ND (i.e., not done) or NS (i.e., no sample),
2. A relevant deviation in sampling time (as defined in ICH guideline M4S(R2)) is of sufficient concern or a concentration has been flagged anomalous by the pharmacokineticist.

6.3. Pharmacokinetic Parameters

Actual PK sampling times will be used in the derivation of PK parameters.

If a PK parameter cannot be derived from a subject’s concentration data, the parameter will be coded as NC (i.e., not calculated). Note: NC values will not be generated beyond the day that a subject discontinues.

In summary tables, statistics will be calculated by setting NC values to missing, and statistics will be presented for a particular dose with 3 evaluable measurements.

If an individual subject has a known biased estimate of a PK parameter (due for example to an unexpected event such as vomiting before all the compound is adequately absorbed in the body), this will be footnoted in summary tables and will not be included in the calculation of summary statistics or statistical analyses.

7. STATISTICAL METHODOLOGY AND STATISTICAL ANALYSES

7.1. Sample Size Determination

Given the relatively high PK variability observed in a previous bioavailability study employing another route of administration, N=8 is considered the minimum acceptable sample size, and N=12 would be sufficient as defined by clinical and analytical standards (EMA: Note for guidance on the investigation of bioavailability and bioequivalence, CPMP/EWP/QWP/1401/98). In preparation N=4 dropouts, we determined that N=16 subjects is sufficient.

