3.1. Study Design

This is a single-blind, randomized, two-arm, dose-response study of DMT and harmine in healthy subjects.

N = 16 healthy female and male subjects (25-45 y) with no current or previous history of neurological or psychiatric disorder and no first-degree relatives with history of Axis-I psychiatric disorder will be recruited by medical screening. In this open-label pilot study, acute subjective effects and blood samples following the administration of escalating doses of DMT and harmine as a sublingual single preparation are measured. Additionally, on the fourth test day participants will receive either DMT or harmine only as a sublingual preparation according to their arm allocation. The study will be conducted at the Psychiatric University Hospital Zurich (PUK). Study participants will undergo a telephone and medical screening before enrolment to the study. Possible doses for each study day are given in section 3.4. Blood sampling and pharmacokinetic modeling, as well as assessing vital signs and the intensity of subjective effects follows the timeline shown in the figure below. Blood is sampled 15 times over the course of 24 h. Vital signs and the intensity of subjective effects will be monitored throughout the study at baseline, 0, 20, 40, 60, 85, 120, 150, 180, 240, 300, 540, 1440 (= 24h) after administration. This protocol is used for all 6 pilot days. ECG is measured

at baseline, 75, 150, 300, 540, and 1440 min after administration. Body temperature is measured at baseline, 75, 180, 300, 540, and 1440 min after administration. Semistructured interviews will be conducted on the second study day towards the end of the study day. The 'Aliveness' Task will be conducted on the first 3 study days at ~100 min after substance administration. Participants will be released at the end of the study day but will come back the following day for their assessments 24 hours after first substance administration.

The daily schedule for study events are displayed in Figure 3. A detailed description of the schedule for the study participation and procedures is provided in the accompanying protocol (BASEC-Nr. 2022-00973).

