3.1.2. Non-identical cross-over period

A non-identical cross-over paradigm will be applied on days 5 and 6. This scheme will allow us to explore DMT/harmine in additional combinations which were explored in the initial titration phase so that all individuals in both treatment arms have been exposed to all combinations, except for the DMT-only and Harmine-only conditions which are unique to each arm. The timeline for this study is shown in figure 2.

[figure not shown]

Figure 1. Dose ratios for the dose-finding study. The sublingual formulation is administered in a ratio-varying manner on six study days in two arms that differ in the order of substance administrations (equivalent to a cross-over design). On the 4th study day, participants will either receive DMT or harmine only, depending on the arm they are allocated to.

RE01 - DHTP - Statistical Analysis Plan

[figure not shown]

Figure 2. Study flow chart for the dose-finding study.

[figure not shown]

Figure 3. Timeline of drug administration and assessments for each study day.

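### Does the single sample-size justification in SAP Section 7.1 fail for the DMT-only and harmine-only conditions?

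*SAP*

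**What the plan says.** Section 7.1 of the SAP refers to high PK variability in a previous bioavailability study and states: "N=8 is considered the minimum acceptable sample size, and N=12 would be sufficient as defined by clinical and analytical standards". It continues: "In preparation N=4 dropouts, we determined that N=16 subjects is sufficient". No condition, arm or analysis set is named.

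The design sections describe who receives what. Section 3.1.1 says "We will test 7 different dosing conditions with varying DMT:harmine ratios during the first 4 days". Section 3.1 says that "on the fourth test day participants will receive either DMT or harmine only as a sublingual preparation according to their arm allocation". Section 3.1.1 adds: "The DMT/harmine only condition is the only one that is exclusive for one of the two study arms". Section 3.1.2 says that by the end of days 5 and 6 everyone has had every combination, "except for the DMT-only and Harmine-only conditions which are unique to each arm".

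The primary PK endpoints in Section 5.1 are worded for the combined product. For Cmax the wording is "Dose-dependent changes in Cmax of several doses of combined DMT & Harmine", and AUC and half-life follow the same pattern. Sections 5.3.4 and 7.3.1.1 summarise PK separately for each dose combination, and Section 7.2 anticipates no formal hypothesis testing.

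**The concern.** Because PK is summarised condition by condition, the n that governs precision is the n in each condition. Section 7.1 sets two adequacy thresholds, 8 and 12, without saying where they apply. A reader could carry them over to all seven conditions, and for two of the seven the figure of 12 is out of reach.

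Two things would then be at stake. The first is the precision of the single-drug PK summaries, in a study whose size is justified by high PK variability. The second is how the DMT-only day is read. Section 3.1.1 gives its reason: "this is done to further clarify if DMT alone is capable of inducing its effects with routes other than intravenous administration or inhalation". If few or no effects were seen in a handful of subjects, someone relying on an unqualified claim of sufficiency might take that as stronger evidence than it is.

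**Working it through.** **The plan's own figure (Section 7.1).** Sufficient number 12, dropout allowance 4: 12 + 4 = 16. It reproduces exactly. The allowance is 4/16 = 25% of those enrolled, and 12/(1 − 0.25) = 16 as well.

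**Conditions (Sections 3.1.1 and 3.1.2).** 7 conditions − 2 single-drug conditions = 5 combinations. Each arm receives 3 on days 1–3 and 2 on days 5–6, which is 5. Adding the single-drug day gives 6, matching the six study days.

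**Shared combinations.** 16 planned, and 16 − 4 = 12 after the allowed dropouts. The justification works here.

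**Single-drug conditions, any allocation.** Each subject is assigned one of the two, so n(DMT-only) + n(harmine-only) ≤ 16.
- Both at 12 needs 2 × 12 = 24, which is impossible.
- Both at 8 needs 2 × 8 = 16, so an 8:8 split and no loss before day 4.
- If all 4 dropouts come before day 4, the two total 12, so at least one is below 8 under every split.

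**Single-drug conditions, assuming 1:1 allocation and dropouts falling at random across arms.** With k dropouts before day 4, the mean n per condition is 8 − k/2.

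| k | mean n per condition | mean n of the smaller condition |
|---|---|---|
| 0 | 8 | 8 |
| 1 | 7.5 | 7 |
| 2 | 7 | 6.53 |
| 3 | 6.5 | 5.80 |
| 4 | 6 | 5.35 |

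For k = 4 there are C(16,4) = 1820 equally likely sets of dropouts. For the smaller condition:
- n = 6: C(8,2)² = 784, and 784/1820 = 43%
- n = 5: 2 × C(8,1) × C(8,3) = 896, and 896/1820 = 49%
- n = 4: 2 × C(8,4) = 140, and 140/1820 = 8%

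**PK precision.** The SAP gives no CV, so 30%, 50% and 70% are assumed. The 95% CI for a geometric mean is the estimate multiplied and divided by exp(t(0.975, n−1) × √ln(1 + CV²) / √n).

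| CV | n = 12 | n = 8 | n = 6 |
|---|---|---|---|
| 30% | 1.21 | 1.28 | 1.36 |
| 50% | 1.35 | 1.48 | 1.64 |
| 70% | 1.49 | 1.70 | 1.94 |

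**No effect seen in any DMT-only subject.** This treats an effect as a yes/no outcome, which the visible SAP does not define. The exact two-sided 95% upper limit for 0 of n is 1 − 0.025^(1/n): 26% at n = 12, 37% at n = 8 and 46% at n = 6.

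**The SAP's own reporting rule.** Section 6.3 presents PK summary statistics for a dose when 3 evaluable measurements exist. With 1:1 allocation and four early dropouts, the smallest possible attendance is 8 − 4 = 4. This is still above 3, provided at least three of those subjects have evaluable profiles.

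**The case for a change.** The strongest case for changing the text is that Section 7.1 itself chose 8 and 12 as adequacy standards, and the bound of 16 for the two single-drug conditions needs no assumption. The plan counts those conditions among the seven it tests, gives the DMT-only day a scientific purpose, and budgets for dropouts that could take one of them below its own minimum. If the section is meant only for the combinations, saying so costs one sentence.

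The counting stands, and so does the observation that Section 7.1 carries no scope clause. What does not stand is that the section is therefore wrong. It makes no claim about each condition; that claim has to be read into it before it can be shown to fail. A sample-size paragraph is ordinarily read against the primary endpoints, and here the PK ones are defined on DMT and harmine given together.

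The shortfall figures also depend on matters outside the SAP. The allocation ratio is not stated in it, and only losses before day 4 count, whereas the SAP gives no timing for dropouts. The limits for zero responders need a yes/no outcome, whereas Section 5.1 describes subjective effects as trajectories.

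Nor would the obvious rewrite be safe. Promising about 12 completers for each combination overlooks Section 4.2, where the main PK sets require all three doses, and Section 7.4.3, which treats declining an increment as distinct from dropping out. Evaluable n for a combination can fall below 12 with no more than four dropouts.

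**Conclusion.** No change follows. The study-level arithmetic is correct, and the design delivers it for the conditions on which the primary PK endpoints are defined. What is missing is a clause on scope, and a reader can supply it: Sections 3.1, 3.1.1 and 3.1.2 each say that the single-drug day differs by arm. Table 1 in Section 7.3.1.1 reports N beside the geometric mean and geometric CV% for AUC and Cmax, and N beside the median and range for half-life, so the smaller n will be visible wherever it matters. Nothing is tested, so no error rate or power depends on the point, and a sentence limiting the justification would leave every table and figure as it is. Adding confidence intervals to the single-drug summaries would be a matter of preference.

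The size of what remains: together the two single-drug conditions have at most 16 subjects under any allocation. Assuming 1:1, each starts with 8, which is the stated minimum, and averages between 8 and 6 as dropouts before day 4 go from 0 to 4. At an assumed CV of 50%, the 95% interval for a geometric mean widens from a factor of 1.35 at n = 12 to 1.48 at n = 8 and 1.64 at n = 6. That is a reason to read the day-4 results with their n in view. If the SAP is reopened for other reasons, a sentence noting the smaller, exploratory n of these two conditions would be harmless, provided it does not promise 12 evaluable subjects per combination.
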